#### Events **NOT** meeting the AE definition

- Any Medical or Surgical procedure that occurs during the Trial (the medical condition resulting in the requirement of the procedure will be documented as an AE)
- Anticipated day-to-day fluctuations of pre-existing disease(s) or condition(s) present that do not worsen.
- Surgery planned prior to informed consent to treat a pre-existing condition that has not worsened.

Although these events should not be reported to the Lead Sponsor, these should be recorded in the patient's medical notes according to routine practice.

#### 12.3. Adverse Reaction (AR) or Adverse Drug Reaction (ADR)

An AR is any untoward and unintended responses to an investigational medicinal product or to an experiment and, when an investigational product is concerned, related to any dose administered.

## 12.4. Serious Adverse Events (SAEs) Definition

A serious non-COVID-19 associated adverse event is any untoward medical occurrence that at any dose:

- Results in death
- Is life threatening in the context of "serious" life threatening refers to any event where the participant was at risk of death at the time of the event.
- Requires in-patient hospitalisation or prolongation of existing hospitalisation Hospitalisation for an elective procedure to treat a pre-existing condition which occurred prior to study intervention that has not worsened is not an SAE
- Results in persistent or significant disability/incapacity
- Is a congenital anomaly/ birth defect
- Is another important medical event that may not be immediately life-threatening or result in death or hospitalisation but medical and or scientific judgement has determined the event may jeopardise the participant or may require medical or surgical intervention to prevent one of the other outcomes as listed above. Examples of such events include, invasive or malignant Cancers, intensive treatment in an emergency room or at home for allergic bronchospasm; blood dyscrasias or convulsions that do not result in hospitalisation.)

For this trial, the following events are subjected to the same reporting requirement of SAE:

- Potential drug induced liver injury
- Pregnancy (See pregnancy section below for reporting pregnancies)
- Suspected transmission of an infectious agent via product (where required by the country specific legislation)

## 12.5. Serious Suspected Unexpected Serious Adverse Reaction (SUSAR)

A SUSAR is an adverse reaction, the nature or severity of which is not consistent with the information on the experiment, and, when a clinical trial is concerned, with the applicable Reference Safety Information (RSI).

## 12.6. Collecting and Recording AE and SAE

- All non-COVID-19 associated AEs and SAEs, whether or not they are related to the study intervention or protocol defined procedures must be documented in the patients' medical notes and eCRF. If no diagnosis is available, the Investigator should record each sign and symptom as individual AEs.
- The site will enter the AEs and SAEs into the eCRF as soon as it is known to the Investigator or sub investigator. The eCRF must be updated as soon as additional information is made available to the investor or sub investigator. If the electronic system is unavailable for more than 24 hours, then the site will use the paper form
- Reportable SAEs as defined above will be reported to the Co-Sponsor within 24 hours of the study team becoming aware of the event. SAE details will be included in the Safety Event Report Form (SERF) and the SERF emailed to [contact] or faxed to [name].
- The AEs and SAEs reporting period will be from participant consent until 28 days after randomisation.
- Pregnancy will be also subjected to the same reporting rules of SAE. Pregnancy details will be included in the SERF and the SERF emailed to [contact] or faxed to [name] within 24 hours of the study team becoming aware of the pregnancy.
- All AEs and SAEs will be followed up until resolved or the participant's participation in the study ends (i.e. until the final CRF is completed for that participant).
- When an AE/SAE occurs, it is the responsibility of the investigator or sub investigators to review all clinical information relating to the event.
  - The investigator or sub investigator will attempt diagnose the event based on direct examination and/or other clinical information.
  - The principle investigator must confirm within the SERF the causality assessment with the study drug. If the SAE is assessed as possibly related, probable related or definitely related, the principal investigator must also confirm the event expectedness versus the Reference safety information (refer to section 12.10).
- The Investigator must record follow-up information (related to the reported event) by updating the patient's medical records and the appropriate forms in the (e)CRF. The worst-case severity and seriousness of an event must be kept throughout the trial.
- 2.7 SAEs after the end of the trial: If the Investigator becomes aware of an SAE with suspected causal relationship to the study drug or experiment after the subject has ended the trial, the Investigator should report this SAE as per the process above, within the same timelines as for SAEs during the trial (however there will be not requirement to report the SAE in the eCRF). Reporting requirements to Ethics Committee's (EC's) and Competent Authorities (CA's)

The Investigator is responsible for ensuring that all safety events are recorded in the (e)CRF and reported to the Sponsor in accordance with instructions provided.

The Sponsor will promptly evaluate all SAEs against medical experience to identify and expeditiously communicate possible new safety findings to Investigators, EC's and applicable CA's based on applicable legislation.

#### 12.7.1. Sponsor's reporting of SUSARs

After receiving the SAE report form from the Investigator, the Co-Sponsor has to make a causality (relationship) assessment. The term SADR (Serious Adverse Drug Reaction) is to be used whenever either the Investigator or the Co-Sponsor deems the SAE as possibly or probably related to the study drug.

The Co-Sponsor must evaluate (and document the evaluation of) the expectedness for each SADR against the RSI. In case the event is Unexpected (= a SUSAR) it must be reported by the Co-Sponsor to the EC's, CA's or IRB (following the country applicable legislation) and other participating Investigators within the following timelines:

- **7 calendar days** if fatal or life-threatening event (follow-up information within an additional 8 days)
- **15 calendar days** if non-fatal or non-life-threatening event (follow-up information as soon as possible)

CAs will be notified through the appropriate system (such as Eudravigilance portal in Europe, e-SUSAR portal in UK).

#### 12.7.2. Other Reporting

Any other local reporting requirements other than of SUSAR submission will be outlined in the Pharmacovigilance Management Plan (PVMP) along with the respective timelines for submission.

## 12.8 Grading of Adverse Events

An event is defined as "serious" when it meets at least one of the outcomes as described in the definition of an SAE, not when it is rated as severe.

The severity of all AEs and/or ARs (serious and non-serious) that are reported during the trial should be graded using the toxicity gradings in the Common Terminology Criteria for Adverse Events v5 (CTCAE) November 27, 2017criteria using the following definitions:

- Grade 1: Mild; asymptomatic or mild symptoms; clinical or diagnostic observations only; intervention not indicated.
- Grade 2: Moderate; minimal, local or non-invasive intervention indicated; limiting ageappropriate instrumental Activities of Daily Living (ADL) such as preparing meals, shopping for groceries or clothes, using the telephone, managing money etc.
- Grade 3: Severe or medically significant but not immediately life threatening; hospitalisation or prolongation of hospitalisation indicated; disabling; limiting self-care ADL (bathing,

dressing and undressing, feeding self, using the toilet, taking medications and not bedridden).

Grade 4: Life threatening consequences; urgent intervention indicated.

Grade 5: Death related to AE

A semi colon indicates 'or' within the description of the grade.

#### 12.9 Assessment of Causality

The determination of causal relationship between the study drug and the AE/SAE must be performed by the investigator or sub investigator (medically qualified doctor/appropriately delegated to do so).

The below criteria will be used by the investigator or sub investigator to assess the causality of the AE/SAE in relation to the study drug:

- Unrelated There is no evidence of any causal relationship (e.g. the event occurs prior to dosing)
- Unlikely to be related There is little indication to suggest that there is a causal relationship. The participant's clinical condition or other concomitant treatment is related to the AE/SAE.
- **Possibly related** There is some indication to suggest a causal relationship, however, the participant's clinical condition or other concomitant treatment could explain the event.
- Probably related Reasonable indication to suggest a causal relationship such as a likely reaction of the drug or the event cannot be explained by participants clinical condition or other concomitant treatment.
- **Definitely related** There is clear indication to suggest a causal relationship with the study drug and no other possible explanation available to explain AE/SAE.

#### 12.10 Assessment of Expectedness

The determination of the event expectedness between the study drug and the SAE must be performed by the investigator or sub-investigator (medically qualified doctor).

Only SAEs assessed as Possibly, Probably and Definitely related qualify for expectedness evaluation.

The expectedness evaluation will be performed by using the below indicated Reference Safety Information:

• Favipiravir: Investigator Brochure, Favipiravir, dated 20 March 2020. Section: 7.5. Adverse Reactions

## 12.11 Development Safety Update Report (DSUR)

The Co-Sponsor has the obligation to, once a year throughout the clinical trial (or on request), submit a progress report (i.e. DSUR) to the EC's and CA's containing an overview of all SARs occurred during the

reporting period and taking into account all new available safety information received during the reporting period.

## 12.12 Data Safety Monitoring Board (DSMB)

The DSMB is responsible for safeguarding the interests of study participants, assessing the safety and efficacy of study procedures, and for monitoring the overall conduct of the study. The Lead Sponsor will be responsible for release a DSMB chart and appoint the DSMB members. Where local specific requirements in regard DSMB are expressed by local authorities, these will be captured in the PVMP.

#### 13. STATISTICS AND ANALYSIS

### 13.1 Description of Statistical Methods

The two arms (Favipiravir vs Standard of Care) will be compared with time-to-event analysis using a competing-risks survival regression based on Fine and Gray's proportional subhazards model. All analysis will be performed on an intention to treat basis.

Patient improvement will be monitored for 28 days or until death. It is not expected that any patient will be lost to follow-up, even if discharged home. Kaplan-Meier plots will be constructed showing the probability of survival in each treatment group. Schoenfeld Residuals will be plotted and tested over time to examine the assumption of proportional hazards; with a restricted mean survival time analysis (RMST) as an alternative method for analysis for the proportional hazards assumption is not met.

Similarly, patients who discontinued the clinical trial or administration of the study drug due to worsening of symptoms/lack of efficacy (including patients who switched to rescue therapy) but remain alive will be handled as cases right-censored as of day 28, with no clinical improvement.

Additional secondary analysis of the primary outcome will be undertaken that adjust for, or involves a sub-set of patients, and examines the effect of

- (a) country of recruitment
- (b) time from onset of symptoms (median split)
- (c) limited to those patients with confirmed SARS-COV-2 infection
- (d) by high or low (median split) viral load.
- (e) early or late during recruitment to the study to examine improves in clinical care and understanding.

Other secondary analysis have been pre-specified in the statistical analysis plan and listed on clinical trials.gov. Differences between the two trial arms will be compared by standard and appropriate statistical tests.

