## 6.4. Outcome Measures & Endpoints

Objectives	Outcome Measures/Endpoints
Primary Objective To determine whether early intervention with Favipiravir improves the time to significant improvement in clinical status in patients with COVID-19 infection	Time from randomisation to a sustained clinical improvement (maintained for 24 hours) by two points on a seven-category ordinal scale or to discharge, whichever occurs first(10)  The seven-category ordinal scale:  1: Not hospitalised with resumption of normal activities  2: Not hospitalised, but unable to resume normal  3: Hospitalised, not requiring supplemental oxygen  4: Hospitalised, requiring supplemental oxygen  5: Hospitalised, requiring nasal high-flow oxygen therapy, non-invasive mechanical ventilation or both  6: Hospitalised, requiring ECMO (Extra-corporal membrane oxygenation), invasive mechanical ventilation or both  7: Death(10)

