#### 8.7. Allocation of Intervention

Eligible participants will be randomised 1:1 to one of the two arms using a web-based randomisation portal using blocks of randomly varying length.

An immediate allocation of treatment intervention as well as a participant identification number will be provided by the system to the person entering the data.

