#### Primary outcome measure

The primary end-point of this study is the time from randomisation to a sustained clinical improvement (maintained for 24 hours) by two points on a seven-category ordinal scale or to discharge, whichever happens first (recommended by WHO)(10).

The seven-category ordinal scale (23):

- 1: Not hospitalised with resumption of normal activities
- 2: Not hospitalised, but unable to resume normal
- 3: Hospitalised, not requiring supplemental oxygen
- 4: Hospitalised, requiring supplemental oxygen
- 5: Hospitalised, requiring nasal high-flow oxygen therapy, non-invasive mechanical ventilation or both
- 6: Hospitalised, requiring ECMO (Extra-corporal membrane oxygenation), invasive mechanical ventilation or both
- 7: Death

This study will recruit 500 participants in total. We have chosen a primary outcome measure, previously used in influenza trials, of a 2-point change in a scale of clinical status (13, 14). No simpler continuous measure was considered appropriate due to the heterogeneous clinical presentation of COVID-19 infection at hospital admission. In a trial investigating influenza, significant difference in time to a 2 point improvement on the 7-point scale scoring system has been found, with a difference between groups of 40 patients on combined Favipiravir and Oseltamivir, compared with 128 patients on Oseltamivir only (p=0.0477)(10). PIONEER will have 250 patients in each group and will thus we will be able to detect similar improvements seen with these anti-viral agents (appreciably used in the treatment of influenza infection), at an alpha of 0.05

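### The primary Fine-Gray comparison is stated without baseline ordinal category, although the endpoint depends on it: the test is valid but may give up power

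*Protocol*

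**What the plan says.** Section 13.1 of the protocol gives the primary analysis as follows: "The two arms (Favipiravir vs Standard of Care) will be compared with time-to-event analysis using a competing-risks survival regression". The model is Fine and Gray's. No covariate is named. Adjustment comes afterwards, in a separate list introduced as follows: "Additional secondary analysis of the primary outcome will be undertaken that adjust for, or involves a sub-set of patients, and examines the effect of". The list starts with "a) country of recruitment" and continues with time from symptom onset, confirmed infection, viral load, and early or late recruitment. It contains neither baseline ordinal category nor any other severity measure.

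Section 8.7 describes 1:1 randomisation "using blocks of randomly varying length" and names no stratification factor. Section 13.3 mentions a Cox model that would permit adjustment, but names no variable.

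The primary endpoint (section 6.4) is sustained improvement "by two points on a seven-category ordinal scale or to discharge, whichever occurs first". Sections 8.2 and 8.3 set no limit by oxygen or ventilation status, so patients in any of the hospitalised categories 3 to 6 can enter. Section 13.2 acknowledges the spread: "No simpler continuous measure was considered appropriate due to the heterogeneous clinical presentation of COVID-19 infection at hospital admission". Section 10.1 lists heart rate, respiratory rate and oxygen saturation among the baseline data, but not the ordinal category.

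**The concern.** What counts as the event depends on the starting category.

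- From 3, discharge is enough, although it is a one-point step to category 2.
- From 4, discharge is itself the two-point step.
- From 5, the event can be met in hospital by coming off oxygen (category 3).
- From 6, it can be met in hospital by stepping down to supplemental oxygen (category 4).

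Baseline category is therefore a natural candidate for a strong prognostic factor. In a proportional-subhazards model, leaving out a prognostic baseline factor pulls the estimated ratio towards 1 and lowers power, even when the arms are balanced. If randomisation is not stratified, the design does not prevent chance imbalance on that factor either. What is at stake is efficiency: a real effect of moderate size could be missed although the data needed to detect it better are already being collected.

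**Working it through.** **The plan's own figure.** The 500 patients (250 per arm, alpha 0.05) cannot be reproduced, because section 13.2 states no effect size, power or event count. The only anchor is the influenza result it cites: 40 against 128 patients, p = 0.0477. Taken as two-sided, z = 1.980. With a = 40/168 and d events, the implied ratio is exp(z / √(d·a·(1−a))).

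- All 168 with the event: 168 × 0.1814 = 30.48, and exp(1.980/5.521) = 1.43.
- Half with the event: 84 × 0.1814 = 15.24, and exp(1.980/3.904) = 1.66.

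At 1.43, 500 patients give Schoenfeld power of 81% (50% events) to 98% (100% events). With 400 to 450 events, 80% power needs a ratio of 1.32 to 1.30. Ratios of 1.30 to 1.43 are therefore a reasonable range to examine.

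**Simulation inputs (assumed; the protocol gives none).**

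- Mixes of categories 3/4/5/6: 10/80/8/2%, 25/60/12/3% and 25/45/20/10%.
- Subhazard relative to category 4, for categories 3/5/6: weak 1.3/0.7/0.5, moderate 1.7/0.5/0.25, strong 2.5/0.35/0.12.
- Category 4 control rate: 0.10 per day.
- 500 patients, 28 days, two-sided 5%, 2,000 runs per scenario. With complete follow-up, Fine-Gray is a Cox model that keeps deaths in the risk set to day 28, so times were drawn on that scale.

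**Results at a true within-category ratio of 1.30.**

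| Mix (%) | Gradient | Events | Unadjusted ratio | Power unadjusted | Power adjusted | Loss (points) |
|---|---|---|---|---|---|---|
| 10/80/8/2 | weak | 95.0% | 1.289 | 78.2% | 79.6% | 1.4 |
| 10/80/8/2 | moderate | 94.0% | 1.276 | 73.8% | 81.0% | 7.2 |
| 10/80/8/2 | strong | 92.6% | 1.243 | 63.8% | 77.6% | 13.8 |
| 25/60/12/3 | weak | 95.0% | 1.287 | 78.4% | 81.8% | 3.4 |
| 25/60/12/3 | moderate | 93.4% | 1.261 | 70.5% | 81.2% | 10.7 |
| 25/60/12/3 | strong | 91.4% | 1.218 | 56.0% | 79.3% | 23.3 |
| 25/45/20/10 | weak | 93.4% | 1.277 | 75.2% | 80.4% | 5.2 |
| 25/45/20/10 | moderate | 89.4% | 1.233 | 60.6% | 77.8% | 17.2 |
| 25/45/20/10 | strong | 84.7% | 1.195 | 45.3% | 77.3% | 32.0 |

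**Hand check of the last row.** Events are 0.847 × 500 = 423.5, and power is Φ(ln(ratio) × √423.5 / 2 − 1.960).

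- Adjusted: 0.2624 × 20.58 / 2 = 2.700, so Φ(0.740) = 77%.
- Unadjusted: ln 1.195 = 0.1781, and 0.1781 × 20.58 / 2 = 1.833, so Φ(−0.127) = 45%.

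Both agree with the simulation: the loss is explained by the attenuated ratio.

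**At a ratio of 1.43**, for the three mixes in the same order:

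- weak: 96.1 to 96.9%, 96.2 to 97.0%, 94.4 to 97.3%;
- moderate: 94.9 to 97.0%, 92.0 to 97.0%, 85.5 to 96.8%;
- strong: 91.4 to 98.2%, 81.9 to 97.0%, 68.6 to 95.6%.

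**At a ratio of 1.35**, with log-rank tests, no deaths simulated and a 20/50/25/5% mix:

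- relative rates 2/1/0.45/0.2: 71% unstratified against 87% stratified;
- relative rates 1.5/1/0.6/0.35: 81% against 88%;
- relative rates 1.2/1/0.8/0.6: 88.4% against 88.9%, so almost nothing is lost.

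**Type I error** (3,000 runs each): 5.0% unadjusted and 4.7% adjusted for the 25/60/12/3% mix with a moderate gradient; 5.1% and 5.4% for the 25/45/20/10% mix with a strong gradient.

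**The case against.** The strongest reply is that section 13.1 never calls the primary model unadjusted, that covariates are commonly left to the SAP, and that an arm-only test is valid. Part of this stands. The SAP is not shown and may already name the covariate, and silence in section 8.7 does not prove that randomisation is unstratified. However, section 13.1 does more than stay silent: it states a two-arm comparison and places adjustment in an explicit secondary list from which the variable that defines the event is absent. It refers only other secondary analyses to the SAP.

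A reader might also infer more than the documents support.

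- *The unadjusted result would be biased or the error rate inflated.* It would not: type I error stays near 5%. The lower pooled ratio is largely the difference between a marginal and a within-category effect, not an error.
- *Pooling would create non-proportionality that makes the plan switch to restricted mean survival time.* The effect is minor. At a ratio of 1.35 with the steepest of the three rate sets, the pooled ratio was about 1.31 before day 7 and 1.22 after. A Schoenfeld-type test at 5% rejected in 7.3 to 8.1% of trials there, and in 5.7 to 6.4% with the middle set.
- *Each category has its own event, so rates must differ strongly.* Categories 3 and 4 share discharge as the event, and a different event definition does not by itself imply a different rate. In-hospital improvement from category 5 could even narrow the gap.

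**Conclusion.** The point holds as a matter of efficiency. The primary comparison as stated is valid but does not use the one baseline variable on which the endpoint itself depends. With 250 per arm and within-category ratios of 1.30 to 1.43, the power given up is about 0 to 5 points if category is weakly prognostic, 2 to 17 if moderately so and 7 to 32 if strongly so. The low ends of the moderate and strong ranges come from the ratio of 1.43; at 1.30 alone the three ranges are about 1 to 5, 7 to 17 and 14 to 32.

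All these figures rest on assumed mixes, rates and effect sizes. The protocol supports no particular value, and the loss could be negligible if nearly everyone starts in one category or the gradient is flat. Because section 13.2 states no target effect or power, no documented margin is available to absorb a loss.

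**What to change.** In section 13.1, state that the primary Fine-Gray model includes baseline ordinal category (3, 4, 5, 6) at randomisation. Choose in advance whether it enters as a stratum or as a covariate, and how a category with no events is handled. Report the model without it as supportive. Add the category at randomisation to the baseline list in section 10.1. If the SAP already does this, bring section 13.1 into line with it. Age and country are not needed for this fix.

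No new measurement should be required: the baseline category must be known to score the primary endpoint and the change-from-baseline secondary endpoint in section 6.4. There are two costs. The subhazard ratio becomes a within-category (conditional) effect and has to be reported as such. The change also comes late in an open-label trial: enrolment began in May 2020, this version is dated April 2021, and section 13.3 plans an interim analysis from 90 patients. It therefore needs a dated justification, and it must be finalised before those who decide it have seen comparative data.

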#### 9.3. Treatment Administration

The participants' hospital clinicians are responsible for the administration of the allocated treatment and are free to modify or stop study treatment if clinically necessitated, without the need for the patient to withdraw from the study. Study treatment medication will be subject to the standard local pharmacy reviews, which will guide modifications to both the study treatment (i.e. dose adjustment for renal impairment) and the use of concomitant medication (e.g. in the case of potential drug interactions).

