#### 9.5. Potential Benefits

Steroids have been shown to be effective in treating patients with COVID-19 on oxygen and there is also some evidence that other treatments such as the antiviral medicine called Remdesivir may help patients that are severely affected. Early intervention with Favipiravir, has the potential to improve outcomes in those with COVID-19 infection.

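### Section 13.1 records patients who stop study drug for worsening, or who are rescued, as unimproved to day 28 even when improvement was observed, with a bias that depends on how these rates differ between arms

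*Protocol*

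**What the plan says.** Section 6.4 defines the primary endpoint as "Time from randomisation to a sustained clinical improvement (maintained for 24 hours) by two points on a seven-category ordinal scale or to discharge", whichever comes first. Stopping treatment and receiving rescue are not part of it.

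Section 13.1 specifies a "competing-risks survival regression based on Fine and Gray's proportional subhazards model" and states: "All analysis will be performed on an intention to treat basis". It adds that improvement is monitored for 28 days or until death and that no loss to follow-up is expected. It then sets a rule for "patients who discontinued the clinical trial or administration of the study drug due to worsening of symptoms/lack of efficacy", and a parenthesis extends the group to those moved to rescue. Everyone in this group "but remain alive will be handled as cases right-censored as of day 28, with no clinical improvement".

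Section 9.3 says that clinicians are "free to modify or stop study treatment if clinically necessitated, without the need for the patient to withdraw from the study". Section 8.6 asks that the outcome be documented, where possible, even after withdrawal. Section 10.2 collects routine inpatient data to day 28 or discharge, including changes in ordinal score lasting more than 24 hours. Section 7 describes an open-label trial of favipiravir plus standard of care against standard of care, without placebo.

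**The concern.** The rule replaces an observed outcome with an assumed failure because of a treatment decision made after randomisation. It sits among the primary-analysis methods and is not labelled a sensitivity analysis. In effect it adds a treatment-failure component that the endpoint definition does not contain.

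One of its triggers, stopping study drug, exists in one arm only. Another, rescue therapy, is undefined in the protocol and is decided with the arm known. If the share of patients caught differs between arms, the primary subhazard ratio (sHR) shifts for reasons unrelated to how quickly patients improve. That could produce apparent harm, hide a true benefit, or produce apparent benefit.

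**Working it through.** **1. One patient followed through the text.** A favipiravir patient worsens, stops the drug for lack of efficacy, stays in the study as Section 9.3 allows, recovers and is discharged on day 15. Under Section 6.4 this is an event on day 15. Under Section 13.1 it is no event, with follow-up to day 28. Both readings cannot hold in the primary analysis. A control patient with the same course, who neither leaves the trial nor is rescued, counts as an event on day 15.

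**2. Which trigger can occur where.**

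| Trigger (for worsening or lack of efficacy) | Favipiravir | Standard of care |
|---|---|---|
| Stops study drug | yes | no study drug to stop |
| Leaves the trial | yes | yes |
| Switches to rescue | yes | yes |

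**3. Inputs.** From Section 13.2: 250 per arm and alpha 0.05 (taken as two-sided, so 2.5% in each direction). The protocol gives no rate of stopping, rescue or later improvement, and no hazard ratio, event proportion or power. There is therefore no protocol figure for this effect to reproduce. Assumed:
- p = 75% or 85% of controls improve by day 28.
- A fraction f of an arm is caught by the rule.
- A share g = 50–70% of those caught would be seen to improve by day 28.
- The subhazard is constant and follow-up is complete.

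**4. Check by hand.** In a Fine–Gray analysis with complete follow-up, a patient with no event stays in the risk set to day 28. The rule therefore simply removes events. Take f = 5% in the favipiravir arm only, g = 70%, p = 85% and no true effect.
- Events removed: 250 × 0.05 × 0.70 = 8.75, out of 250 × 0.85 = 212.5.
- Recorded improvement by day 28: 0.85 − 0.035 = 0.815.
- If the removed events are a random draw of improvers, the favipiravir incidence curve is multiplied by c = 1 − fg/p = 1 − 0.035/0.85 = 0.9588.
- The subhazard ratio at time t is c(1 − F(t)) / (1 − cF(t)), where F is the control incidence. It starts at 0.959 and reaches 0.9588 × 0.15/0.185 = 0.777 at day 28.
- With p = 75%, c = 0.9533 and the ratio runs from 0.953 to 0.9533 × 0.25/0.285 = 0.836.

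The model averages over these values, so an estimate a little above 0.9 is expected.

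**5. Simulation, 250 per arm, no true effect.** Unless noted, removed events are a random draw of improvers, g = 70%, p = 75–85%, with 4,000 trials per scenario.

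| Caught: favipiravir / control | Estimated sHR | False harm | False benefit |
|---|---|---|---|
| 0 / 0 | 1.00 | 2.1–2.2% | 2.3–2.6% |
| 5% / 0 | 0.91–0.92 | 13–15% | 0.2% |
| 10% / 0 | 0.84 | 38–44% | 0% |
| 10% / 10% | 1.00 | 2.2% | 2.5–2.6% |
| 5% / 10% | 1.09 | 0.2% | 12–13% |

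If removed events come only from patients improving after day 5 (p = 85%, g = 50–70%), 5% / 0 gives sHR 0.95–0.93 and false harm 8–12%; 10% / 0 gives 0.89–0.85 and 21–36%.

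**6. True sHR 1.3, same model as the table.** Without the rule, power is 73–79%. At 5% / 0 the estimate is 1.17–1.18 and power 39%. At 10% / 0 the estimate is 1.06–1.08 and power 9–12%. At 10% / 10% the estimate is 1.25–1.28 and power 65–66%.

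**The case against.** The strongest reply is that this is a familiar conservative treatment-failure rule and that its effect is unknown. Much of that stands.

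- **Scope.** A reader might infer that everyone who stops favipiravir is scored as a failure. The text covers stopping for worsening or lack of efficacy; stopping for toxicity or a drug interaction is outside it.
- **Direction.** A reader might infer a bias against favipiravir because only that arm has a drug to stop. That is true of one trigger out of three. A rescued control is also scored as unimproved.
- **Size.** The large figures need one arm affected and the other untouched. With g = 50%, 7% against 5% caught gives a null sHR of 0.98 and 4.3% false harm, as does 2% against 0.
- **Intention to treat.** All patients stay in their randomised arm, so the analysis set is still intention to treat. What is lost is the use of observed outcomes whatever treatment was received.
- **Section 9.3.** It says nothing about scoring, so it does not contradict the rule. It shows only that drug-stoppers can remain in the study, where their outcome can be seen.
- **Steroids.** Section 9.5 says "Steroids have been shown to be effective in treating patients with COVID-19 on oxygen" but does not call them rescue, and both arms receive standard of care. The protocol does not show that starting them triggers the rule, and a definition of rescue may be in the SAP.
- **Patients who leave while worsening.** Their outcome may be unobtainable. Censoring them at last contact would assume that they improve like those who stay, which is informative censoring. Carrying them to day 28 as unimproved is defensible.

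The rule may have been meant only for missing outcomes. The sentence does not say so: it names patients who stop drug or switch to rescue, without requiring that their outcome be unknown.

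**Conclusion.** The point holds for patients whose outcome is observed. Section 13.1 sets a primary-analysis rule that overrides observed events, and this cannot be reconciled with the Section 6.4 endpoint or with an intention-to-treat comparison of outcomes monitored for 28 days.

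The bias depends on the unknown difference between arms in the share caught. It goes against favipiravir if drug stopping dominates and towards it if rescue is more common on standard care. If the shares are equal there is none under the null, though some power is lost under a true effect. Modest imbalance is enough to matter: 5% against none moves the null sHR to about 0.91–0.95 with 8–15% false harm, and 5% against 10% moves it to about 1.08–1.09 with about 12–13% false benefit (70% later improving). All sizes rest on assumed rates. The conflict in the text does not.

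**What to change.** Amend Section 13.1 as follows.

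1. **Primary analysis.** Count the observed date of sustained two-point improvement or discharge up to day 28 for every randomised participant in both arms, whether or not study drug was stopped or rescue given. Treat death as the competing event.
2. **Unknown outcomes.** Restrict the rule of no improvement to day 28 to participants who left the trial because of worsening and whose later outcome is truly unknown. Vary that assumption in a sensitivity analysis.
3. **Treatment-failure rule.** Keep the present rule, if wanted, only as a sensitivity analysis, with a trigger that is defined identically and can occur in both arms. Report the number caught by arm.

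The cost is one paragraph of wording, carried into the SAP. No new data are needed for participants still followed. For those who leave, Section 8.6 already asks that the outcome be documented where possible.
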